#### Imputation of Missing Efficacy Data

The primary method of handling of missing efficacy data will utilize Multiple Imputations (MI). Last observation carried forward (LOCF) method will be used as supportive analysis of the primary and secondary endpoints. For sensitivity analysis of the primary and secondary endpoints, missing data will be imputed as Treatment Failures (TF). Only missing data up to Week 12 will be imputed. Missing data at the Week 16 Follow-up visit will be analyzed as Observed Cases (OC) only.

**MI:** For the MI model, 100 imputations will be generated using PROC MI of SAS. Fully Conditional Specification (FCS) model using the regression method will be used with the response (e.g., PGA score) at prior post-baseline visits, baseline PGA score, baseline value of the corresponding endpoint, and treatment group as covariates, The ROUND and MINIMUM options will be utilized to ensure imputed values are non-negative integers. The seed to be used in all MI model is 20180330.

One set of MI datasets will be generated for the PGA scores, PASI scores and %BSA results separately. Response status (Yes, No) will be derived from the imputed scores in each MI dataset. Analysis of each primary, secondary and exploratory outcome will then be performed for each of the relevant MI datasets. The results of the 100 analyses will be transformed into a normal statistic and combined into a single analysis using PROC MIANALYZE.

Example SAS code for the PGA scores is as follows:

```
PROC MI DATA = PGA1 OUT = PGA2 SEED = 20180330 NIMPUTE = 100 NOPRINT;  
  CLASS TRTPN BASEPGA;  
  FCS LOGISTIC(BASEPGA = TRTPN / DETAILS);  
  FCS REG(PGA3 = TRTPN BASEPGA / DETAILS);  
  FCS REG(PGA4 = TRTPN BASEPGA PGA3 / DETAILS);  
  FCS REG(PGA5 = TRTPN BASEPGA PGA3 PGA4 / DETAILS);  
  FCS REG(PGA6 = TRTPN BASEPGA PGA3 PGA4 PGA5 / DETAILS);  
  VAR TRTPN BASEPGA PGA3-PGA6;  
RUN;
```

The imputation models may be modified based on the actual data if there is an issue in model convergence.

**LOCF:** The last observed value will be carried forward for any subsequent missing values. Baseline values will not be carried forward.

**TF:** missing data will be imputed as treatment failures for responder endpoint.

Missing functional outcomes, quality of life endpoints or safety endpoints will not be imputed.

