10.6. Handling of Missing Data

Every effort will be made to collect complete data at all visits.

The primary method of handling of missing data will utilize Multiple Imputations (MI). For sensitivity analysis, Treatment Failure (TF) will be imputed for missing data.

For the MI model, 100 imputations will be generated using PROC MI of SAS. Fully Conditional Specification (FCS) model using the regression method will be used with the response (eg, PGA score) at prior post-baseline visits, baseline strata, and treatment group as covariates, The ROUND and MINIMUM options will be utilized to ensure imputed values are non-negative integers. The seed to be used is 20180330. The results of the 100 analyses will be transformed into a normal statistic and combined into a single analysis using PROC MIANALYZE.

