## 12.8 Efficacy Analyses

All efficacy outcomes will be analyzed in the ITT population. Only the primary and secondary efficacy endpoints will be analyzed in the PP population as supportive analyses, as summarized in the Table below.

Efficacy Endpoints	Primary	Sensitivity Analysis
--------------------	---------	----------------------

	Analysis	
Primary Endpoint 
 
PGA response at Week 12
 
	ITT, MI	ITT, OC ITT, TF ITT, LOCF PP, OC
Secondary Endpoints Categorical Endpoint: 
 
PASI-75 at Week 12
 
PGA 0 or 1 at Week 12
 
PASI-90 at Week 12
 
 Continuous Endpoint: 
 
Change in %BSA at Week 12
 
	ITT, MI	ITT, OC ITT, TF (categorical endpoint) ITT, LOCF PP, OC
Exploratory Endpoints 
 
Time to PGA response
 
	ITT, OC	N/A
Exploratory Endpoints 
 
PGA 0 or 1 at Weeks 2, 4, and 8
 
PGA response at Weeks 2, 4, and 8
 
Change in PASI from Baseline at Weeks 2, 4, 8, and 12
 
% change in PASI from Baseline at Weeks 2, 4, 8, and 12
 
PASI-50 at Weeks 2, 4, 8, and 12
 
PASI-75 at Weeks 2, 4, and 8
 
PASI-90 at Weeks 2, 4, and 8
 
Change in %BSA from Baseline at Weeks 2, 4, and 8
 
% change in %BSA from Baseline at Weeks 2, 4, 8, and 12
 
	ITT, MI	ITT, OC
Other Endpoints 
 
Change from Baseline in Peak NRS at Weeks 2, 4, 6, 8, 10, 12 and 16
 
% change from Baseline in Peak NRS at Weeks 2, 4, 6, 8, 10, 12 and 16
 
Peak NRS 4-point Responder at Weeks 2, 4, 6, 8, 10, 12 and 16
 
Change from Baseline in DLQI at Weeks 4, 12, and 16
 
% change from Baseline in DLQI Total Score at Weeks 4, 12 and 16
 
Change from Baseline in PSD at Weeks 2, 4, 8, 12, and 16
 
% change from Baseline in PSD Total Score at Weeks 2, 4, 8, 12 and 16
 
Change from Baseline in SF36 at Weeks 4, 12, and 16
 
	ITT, OC	N/A

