### **12.11 Additional Analyses - COVID-19**

In order to describe the impact of COVID-19 on current study, the following disposition events will be summarized in the tables separately:

- Subjects discontinued from the treatment/study as a result of a positive COVID-19 diagnosis.
- Subjects discontinued from the treatment/study due to other reasons related to COVID-19. This is excluding COVID-19 diagnosis but may include reasons such as site closure, travel restrictions, fear of infection, etc.
- Subjects with study visits altered (including modified in-clinic visit, virtual and phone visits) and missed due to COVID-19

COVID-19 related protocol deviations will be summarized separately. The impact of COVID-19 (including protocol deviation, visit alteration, treatment/study discontinuation and diagnosis of COVID-19) will also be flagged at subject-level in a data listing. Subject profile will be used to compile all COVID-19 related information for affected subjects.

An additional sensitivity analysis of the primary endpoint will be added in the ITT population based on OC only and excluding any virtual PGA assessments at Week 12.

Also, all COVID-19 related symptoms and confirmed cases occur during the study will be reported as AEs and included in the summaries.

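### The imputation models for Weeks 2, 4 and 8 ignore later visits that the subject attended; the loss is small and confined to exploratory endpoints

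*SAP*

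**What the plan says.** The SAP text on missing efficacy data names as covariates treatment group together with these: "with the response (e.g., PGA score) at prior post-baseline visits, baseline PGA score, baseline value of the corresponding endpoint". Protocol 10.6 has the same limit: "at prior post-baseline visits, baseline strata, and treatment group as covariates".

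The example code for PGA follows the text, visit by visit:

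- Week 2: "FCS REG(PGA3 = TRTPN BASEPGA / DETAILS", with no other post-baseline visit.
- Week 4: "FCS REG(PGA4 = TRTPN BASEPGA PGA3 / DETAILS", which adds Week 2.
- Week 8: "FCS REG(PGA5 = TRTPN BASEPGA PGA3 PGA4 / DETAILS", which adds Weeks 2 and 4 but not Week 12.
- Week 12: "FCS REG(PGA6 = TRTPN BASEPGA PGA3 PGA4 PGA5 / DETAILS", which uses all other imputed visits.

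The text applies the rule to PASI and %BSA as well, each with its own set of imputed data. Imputation runs to Week 12; Week 16 is analysed as observed. The one stated ground for altering the models is a convergence problem.

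The table in SAP 12.8 gives ITT with multiple imputation as the main analysis, and observed cases as the sensitivity analysis, for the early-visit endpoints on all three scales, for example "PGA response at Weeks 2, 4, and 8". SAP 12.8.2 confirms the imputation approach for exploratory proportions and continuous outcomes.

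**The concern.** Models that condition only on the past suit monotone dropout, where nothing is observed after the gap. Fully conditional specification is meant for the other pattern, in which a subject misses one visit and attends a later one. Take a subject scored PGA 1 at Weeks 8 and 12 who missed Week 4. The plan draws the Week 4 score from treatment, baseline and Week 2, so the draw can sit oddly beside the subject's own later scores.

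Two things could suffer. The first is precision: the imputed score is noisier than the data allow. The second is bias: if missing a visit is related to severity that shows up later, the later score is what would make the missingness ignorable, and the model leaves it out. The early-visit analyses contribute to the secondary objective of describing efficacy over time.

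**Working it through.** **The plan's own figures.** The plan gives no figure on this point. Its power statement reproduces (40% vs 15%: above 99.9%; 35% vs 20%: 93.8% by exact Fisher and 94.5% by the pooled normal formula, against a stated figure of just over 94%), but nothing below rests on it.

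**Does cycling bring later visits in?** No. An explicit covariate list in an FCS REG statement confines that variable's model to the listed effects. No list for Week 2, 4 or 8 contains a later visit, so iterating the chain does not supply one.

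**Inputs.** From the SAP: 333 and 167 subjects, and up to 25% lost by Week 12. Assumed, because the documents are silent: the between-visit correlation ρ and the share m of subjects missing only the visit in question.

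**Residual variance of one missed score** (score variance set to 1, first-order autoregressive correlation):

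- earlier visits only: 1 − ρ²
- all other visits: (1 − ρ²)/(1 + ρ²)
- reduction: ρ²/(1 + ρ²)

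**Standard error of a visit mean**, proportional to √(1 + [m/(1 − m)] × residual variance). For ρ = 0.6 and m = 10%, m/(1 − m) = 0.111, and the ratio is √[(1 + 0.111 × 0.64)/(1 + 0.111 × 0.471)] = √(1.0711/1.0523) = 1.0089, or 0.89% extra.

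| ρ | Earlier only | All visits | Reduction | Extra SE, m = 5% | Extra SE, m = 10% |
|---|---|---|---|---|---|
| 0.5 | 0.75 | 0.60 | 20% | 0.38% | 0.78% |
| 0.6 | 0.64 | 0.47 | 26% | 0.43% | 0.89% |
| 0.7 | 0.51 | 0.34 | 33% | 0.43% | 0.89% |
| 0.8 | 0.36 | 0.22 | 39% | 0.36% | 0.76% |

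**Other correlation structures.**

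- Equal correlation between all visits gives the smallest loss: at Week 8 with ρ = 0.8, residual variance falls from 0.262 to 0.247, which is 0.08% of SE at m = 10%.
- A baseline correlated only 0.3 with each visit gives the largest, at Week 2. Residual variance is 1 − 0.3² = 0.91 without later visits and 0.72 to 0.36 with them. At 0.36, the extra SE is 2.9% at m = 10%.
- Over all structures tried, the range is 0.04% to 1.4% at m = 5% and 0.1% to 2.9% at m = 10%.

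**Simulation.** 333 vs 167 subjects, 25% monotone dropout plus intermittent gaps, 20 imputations, 150 replicates, correlation 0.6 only. Error is the estimated risk difference minus the one from the same simulated trial with nothing missing.

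- Gaps completely at random, 5%: root mean squared error at Weeks 2, 4 and 8 went from 0.0088, 0.0137 and 0.0170 to 0.0086, 0.0125 and 0.0162 with all visits (2% to 9% lower).
- Gaps completely at random, 15%: 0.0117, 0.0168 and 0.0207 went to 0.0104, 0.0159 and 0.0196 (5% to 11% lower).
- The total standard error after imputation moved by less than 2% in every case.
- Gaps dependent on the Week 12 score, 5% base rate: mean Week 8 error was −0.008 with earlier visits and −0.004 with all visits, against a full-data difference of 0.191. About −0.003 of each was already present with random gaps. Weeks 2 and 4 showed no material change.
- Week 12: root mean squared error went from 0.0214 to 0.0210 (5% random gaps) and from 0.0236 to 0.0226 (15%).

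**The case against.** The strongest reply is that the effect is too small to justify touching a prespecified model. Weeks 2, 4 and 8 are exploratory and outside the fixed testing sequence, and each imputed analysis already has an observed-case companion. That is right about importance. However, an observed-case analysis does not repair the imputation model used in the main analysis.

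A second reply is that gaps followed by attendance may be rare. SAP 12.11 will summarise this group: "Subjects with study visits altered (including modified in-clinic visit, virtual and phone visits) and missed due to COVID-19". A reader might infer that such gaps are certain. The documents do not support that: no rate is given, later attendance is not stated, and an altered or virtual visit may still yield a score. Protocol 4.6.2 has missed visits rescheduled, and SAP 11.4 maps unscheduled assessments into visit windows. The only loss the plan quantifies, up to 25%, is loss to follow-up, which is mostly monotone and leaves no later data to use. So the frequency is unknown and may be low. The possibility remains, since Protocol 4.6.2 lets a subject continue after a missed visit.

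A third reply concerns bias. The COVID-19 reasons that SAP 12.11 lists for discontinuation (site closure, travel limits, fear of infection) have little to do with later severity. This stands for COVID-19 gaps; other reasons for missing a visit are not covered by it.

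Finally, one set of imputed PGA data serves the primary, secondary and exploratory outcomes, so the edit also alters the data behind the primary analysis and makes the models depend on each other across iterations. Both are real but slight costs.

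**Conclusion.** The point holds as a minor inefficiency. Text and code agree, in both documents, in discarding observed later scores whenever a visit is missed and a subsequent one attended. The 20% to 39% figure is the reduction in residual variance of a single imputed score under assumed autoregressive correlations of 0.5 to 0.8; it should not be read as lost precision in any planned estimate. For a visit mean, the cost is about 1% of the standard error at an assumed 10% gap rate (range 0.1% to 2.9%), with a small gain in bias at Week 8 if missingness follows later severity.

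A reader might also infer that the primary result is at risk. It is not to any useful degree. The primary and secondary endpoints are at Week 12, the last imputed visit, whose model already contains every other imputed visit. Week 8 values imputed without Week 12 do feed that model, but the effect in simulation was negligible. Nor does the description of onset rest on these analyses alone: time to PGA response is a Kaplan-Meier and log-rank analysis of observed cases and is unaffected.

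**What to change.** Before unblinding:

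- Expand the three early-visit statements so that each lists every other post-baseline visit to Week 12, for example `FCS REG(PGA4 = TRTPN BASEPGA PGA3 PGA5 PGA6 / DETAILS);`, with the Week 2 and Week 8 statements treated likewise. The Week 12 statement needs no change. Do the same for PASI and %BSA.
- In the SAP text, replace the limit to prior visits by all other post-baseline visits up to Week 12.
- Check convergence of the chain, since the models now depend on one another.
- Record the departure from Protocol 10.6 in SAP section 13, which at present reports no change from the protocol beyond the SF-36 scores and the COVID-19 additions.

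The cost is a wording and code edit. Sample size, the primary test and the testing order stay as they are, and no new data are needed. The downsides are a small change to the prespecified imputation set that also serves the primary analysis, and slightly more dependence on the number of iterations.

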## **10. INTERIM ANALYSIS**

No interim analysis is planned.

## **11. DATA CONVENTIONS FOR ANALYSIS**

### **11.1 General Statistical Principles**

All statistical tests will be performed at the 0.05 (two-sided) level of significance.

All observed and derived variables (e.g., change from baseline, percentage change from baseline, and response status) that are analyzed or summarized will be listed by subject. Descriptive statistics will provide an overview of the efficacy and safety results. For categorical parameters, the number and percentage of subjects in each category will be presented. The denominator for percentage will be appropriate for the purpose of the analysis. For continuous parameters, descriptive statistics will include number of subjects, mean, standard deviation (SD), median, minimum, and maximum.

### **11.2 Study Day**

Day 1 is the date of first study drug administration. As subjects apply study drug under supervision on the day of randomization, this will generally be the day of the Baseline Visit. Study day is calculated relative to the date of Baseline (Day 1).

### **11.3 Baseline and Change from Baseline**

Baseline value is defined as the last non-missing value prior to the first dose of study drug. Change from baseline is defined as the post-baseline value minus the baseline value unless otherwise specified. Percent change from baseline is calculated as follows: Percent change = (Change from baseline / Baseline) \* 100.

### **11.4 Analysis Visit Window**

All efficacy and safety endpoints will be analyzed according to the nominal visits (i.e. actual visit) except for assessments collected on early termination and unscheduled visits. Early termination and unscheduled visits will be re-numbered to an analysis visit based on their windowed visits defined by actual study day. If more than one visit occurs within a single visit window, then the analysis will take the one closest to the target day. If the 2 visits are equidistant from the target day, the visit with later date and time will be used.

The following analysis visit windows will apply to early termination and unscheduled visits:

Visit	Week	Target Day	Analysis Window
2	Baseline	1	On or prior to Day 1
3	2	15	Post first dose – Day 21
4	4	29	Day 22 – Day 42
5	8	57	Day 43 – Day 70
6	12	85	Day 71 – Maximum (last day of treatment + 3 days, Day 87)
7	16	113	> Maximum (last day of treatment + 3 days, Day 87)

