6.3.4. Clinical Safety Laboratory Assessments

All protocol-required laboratory assessments must be conducted in accordance with the Study Reference Manual or Laboratory Manual and the protocol Schedule of Assessments ([Table 1](#)). Laboratory requisition forms must be completed, and samples must be clearly labeled with the subject number, protocol number, site/center number, and visit date. Details for the preparation and shipment of samples will be provided by the laboratory and are detailed in the Study Reference Manual or the Laboratory Manual. Reference ranges for all safety parameters will be provided to the site by the laboratory responsible for the assessments.

A list of clinical laboratory tests and parameters is provided in [Table 3](#).

All laboratory tests with values that are considered clinically significantly abnormal during participation in the study should be repeated until the values return to normal or baseline. If such values do not return to normal within a period judged reasonable by the Investigator, the etiology should be identified, if possible, and the Sponsor notified.

Table 3: Laboratory Tests

Diagnostic Screening Tests		

 • HBsAg • Hepatitis C antibody • Anti-HBc 	
 • Pregnancy tests: (serum at Screening and urine at other visits; women of CBP only) • FSH (as needed in women of non-CBP only) • At the Investigator’s discretion, subjects may be screened for alcohol and illicit drug use. 	
Serum Chemistry		

 • BUN • Creatinine • Glucose (fasting not required) • Sodium • Potassium • Chloride 	
 • Total carbon dioxide • Calcium • AST • ALT • Alkaline phosphatase 	
 • Uric acid • Total bilirubin (+fractionated if required) • Total protein • Albumin
Hematology		

 • Platelet count • RBC count • WBC count (absolute) • Reticulocyte count • Hemoglobin • Hematocrit 	
 • RBC Indices: • MCV • MCH • MCHC • Reticulocyte percentage 	
 • WBC Differential: • Neutrophils • Lymphocytes • Monocytes • Eosinophils • Basophils
Urinalysis		

 • Specific gravity • Microscopic examination (if blood or protein is abnormal) 	
 • Dipstick: pH, Glucose, Protein, Blood Ketones 	

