### **12.9.3 Clinical Laboratory Testing**

All clinical laboratory (hematology, clinical chemistry, urinalysis) values will be listed by subject. The reference normal ranges and reference range indicators (e.g. high, low, normal etc.) will be supplied by the central laboratory and displayed in the data listings. For the purpose of shift table summaries, the central lab reported reference range indicators will be classified as low, normal and high accordingly based on the table below. Change from baseline in abnormality status will be summarized using shift tables. For urinalysis, only lab tests with numeric results reported are included in shift tables. Separate listings will identify subjects with markedly abnormal values. For quantitative measures, observed values and changes in clinical laboratory values will be summarized descriptively by visit and treatment group.

Reference Range Indicator in Shift Tables	Reference Range Indicator Reported by Central Lab
Low	Low, Low Level 1 Alert, Low Level 2 Alert
Normal	Normal
High	High, High Level 1 Alert, High Level 2 Alert

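### SAP 11.4 gives scheduled lab samples no priority over repeats, so a repeat that has normalised can replace an abnormal scheduled value in the by-visit lab summaries

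*SAP*

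**What the plan says.** The opening sentence of SAP 11.4 begins "All efficacy and safety endpoints will be analyzed according to the nominal visits (i.e. actual visit" and then excepts assessments from early termination and unscheduled visits. For those, "Early termination and unscheduled visits will be re-numbered to an analysis visit based on their windowed visits defined by actual study day". Two selection rules follow:

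- The rule for choosing among several records: "If more than one visit occurs within a single visit window, then the analysis will take the one closest to the target day".
- The tie rule, which favours whichever record came second: "If the 2 visits are equidistant from the target day, the visit with later date and time will be used".

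The window table is introduced separately by "The following analysis visit windows will apply to early termination and unscheduled visits". No sentence says that a scheduled record outranks an unscheduled one, and laboratory data are not exempted.

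Protocol 6.3.4 says that lab tests judged clinically significantly abnormal "should be repeated until the values return to normal or baseline".

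SAP 12.9.3 plans descriptive lab summaries by visit and arm. It adds: "Change from baseline in abnormality status will be summarized using shift tables". It does not say whether the shifts are by visit, to the last value or to the worst value. All lab values are listed by subject, and markedly abnormal ones are also listed separately.

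**The concern.** Repeat samples taken under Protocol 6.3.4 exist because an earlier result was abnormal, and the series is meant to end once the value has resolved. A rule that chooses between the two by distance from a target day, with ties going to the later one, can swap an abnormal on-drug result for its normalised repeat.

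The swap matters for three reasons:

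- Clinically significant change from baseline in lab values is a stated safety endpoint (Protocol 2).
- Post-baseline on-treatment labs are scheduled only at Weeks 4 and 12 (Protocol Table 1), so one replaced value is half of a subject's scheduled on-treatment lab record.
- Protocol 1.3.1.2 reports liver findings, and haematological findings secondary to thymic changes, in repeat-dose toxicity studies.

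The SAP protects extremes elsewhere. SAP 12.9.1 classifies each subject by worst grade for treatment-emergent adverse events (TEAEs) and by the most extreme level for adverse events of special interest. Lab tables have no equivalent.

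**Working it through.** The plan states no figure on this point, so there is none to reproduce. The check applies the SAP 11.4 rule day by day.

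**Inputs from the documents**

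- Target days: 29 (Week 4), 85 (Week 12) and 113 (Week 16), from SAP 11.4.
- Visit tolerance: ±2, ±2 and ±4 days, from Protocol 7.3.2, 7.3.4 and 7.4.
- Windows, from SAP 11.4: Week 4 is Days 22 to 42. Week 12 is "Day 71 – Maximum (last day of treatment + 3 days, Day 87"), so it always reaches at least Day 87. Week 16 is anything later.

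**Assumed, because the documents give neither:** the scheduled day is uniform over the tolerance, and the delay to the repeat is uniform over a stated range.

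**Rule.** Let d be the scheduled day minus the target day, and k the delay in days. With both records in one window, the repeat is used if |d + k| ≤ |d|.

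- If d < 0, this means k from 1 to 2|d|.
- If d ≥ 0 and k ≥ 1, it never happens.
- If k = 0 (a same-day repeat recorded as unscheduled), the distances tie and the later time wins.

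**Days on which a repeat replaces the scheduled sample**

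| Visit | Scheduled day | Replacing repeat days |
|---|---|---|
| Week 4 | 27 | 28–31 |
| Week 4 | 28 | 29–30 |
| Week 4 | 29–31 | none |
| Week 12 | 83 | 84–87 |
| Week 12 | 84 | 85–86 |
| Week 12 | 85–87 | none |
| Week 16 | 109 | 110–117 |
| Week 16 | 110 | 111–116 |
| Week 16 | 111 | 112–115 |
| Week 16 | 112 | 113–114 |
| Week 16 | 113–117 | none |

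Example: a scheduled Week 4 sample on Day 27 shows raised ALT.

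- Normal repeat on Day 30: |30 − 29| = 1 is less than |27 − 29| = 2, so the repeat is used.
- Normal repeat on Day 31: 2 = 2, so the later record is used.
- Normal repeat on Day 32: 3 > 2, so the scheduled value stays.

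Visits earlier than the tolerance widen the exposure. A Week 4 sample on Day 24 has d = −5, so any repeat on Days 25 to 34 replaces it.

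**Share of repeated results replaced, Weeks 4 and 12.** There are five scheduled days. d = −2 contributes k = 1 to 4, and d = −1 contributes k = 1 to 2.

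| Assumed delay (days) | Replaced / combinations | Share |
|---|---|---|
| 1–3 | (3 + 2) / (5 × 3) = 5/15 | 33% |
| 1–7 | (4 + 2) / (5 × 7) = 6/35 | 17% |
| 1–14 | 6 / (5 × 14) = 6/70 | 9% |
| 3–14 | 2 / (5 × 12) = 2/60 | 3.3% |
| 5 or more | 0 | 0% |

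At Week 16 there are nine scheduled days. For delays of 1 to 7 days the share is (7 + 6 + 4 + 2) / (9 × 7) = 19/63 = 30%, against 17% at Weeks 4 and 12. That visit is off treatment.

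These are shares of repeated results that are replaced. The loss towards normal is the share multiplied by the proportion of replacing repeats that have already normalised, so each figure is an upper bound under its timing assumption.

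**After the fix.** If the scheduled record is kept whenever it exists, the number of replacing days is 0 in every row.

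**The case against.** The strongest counter-argument is that these abnormalities are already captured by arm. Protocol 6.3.4 asks for repeats only when a result is clinically significantly abnormal. Protocol 8.1.1 uses nearly the same test to make a lab result an adverse event, apart from findings attributable to the underlying disease that are no more severe than expected. Such an event starting after first dose is a TEAE, and SAP 12.9.1 tabulates it by arm at worst grade. This stands. A reader might infer that the abnormal value vanishes from every table by treatment group, or that the safety comparison as a whole is understated. The documents do not support either inference. The TEAE route does not, however, correct the lab tables.

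Other points:

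- **Direction.** The rule chooses by day, not by result. An early repeat may still be abnormal, or worse, and then no abnormality is lost. A reader might infer that every replacement moves the tables towards normal. That is too strong: only a repeat that has already normalised does so.
- **Timing.** Samples are shipped (Protocol 6.3.4) and reference ranges come from a central laboratory (SAP 12.9.3), so repeats within 1 to 3 days may be uncommon. The 33% is the top of an assumed range, not an expectation.
- **Narrower reading.** The windows are said to apply to early termination and unscheduled visits, so the nearest-day rule could be meant to choose only among those. The SAP does not say so, and that reading leaves two records for one visit with no rule for choosing between them. The text needs clarifying either way.
- **Shift tables.** Their basis is unstated, so it cannot be asserted that they lose the value.
- **Descriptive use.** SAP 12.9 plans no formal safety comparison, and SAP 12.9.4 already tabulates markedly abnormal vital-sign changes. Both limit the consequence.

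**Conclusion.** The point holds in a limited form. On its plain text, SAP 11.4 lets a normalised repeat replace an abnormal scheduled lab value in the by-visit summaries, and in the shift tables if these turn out to be by visit. For in-tolerance Week 4 and Week 12 visits, the scheduled sample must come before the target day and the repeat must be at least as near to it, hence within 4 days, or the repeat must be a same-day unscheduled record. Exposure is wider at Week 16 and for visits earlier than the tolerance.

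The share of repeated results replaced at Weeks 4 and 12 lies between 0% and about 33%, depending entirely on the assumed delay. The number of subjects affected cannot be computed, because the documents give no abnormality or repeat-test rates. If tapinarof does cause lab abnormalities, the lab tables would tend to understate the difference from vehicle. The effect is confined to the lab summary and shift tables and does not touch efficacy. It is a modest defect, worth correcting because correction is cheap.

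**What to change.** In SAP 11.4, state that for laboratory and vital-sign summaries the scheduled value is kept when present, and that an unscheduled or early termination value is used only when the scheduled one is missing.

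In SAP 12.9.3, state the basis of the shift tables. Include a shift from baseline to the worst value (lowest and highest) after first dose through Week 12, with unscheduled values included.

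The cost is SAP wording and a small change to the analysis dataset derivation, made before unblinding. No new data are needed. The downside is that reported abnormality counts may rise slightly.
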